Therapeutic plasma exchange (TPE) offers an immediate and scientifically grounded intervention for the removal of a host of pathogenic antibodies and toxic molecules by centrifugal separation of plasma or plasma membrane filtration. Xiao⁵ and colleagues successfully incorporated TPE in the management of a patient with severe CRS following CAR-T treatment in conjunction with Tocilizumab and steroids with daily documentation of cytokine levels.

Precedence for consideration of TPE in a variety of inflammatory dominant disease states is well known. Interest in adjuvant treatment for management of sepsis and multi organ dysfunction is reflected in Busund⁶ and Rimmer⁷ manuscripts. Patel et al⁸ successfully used TPE in three pediatric patients with pH1N1 influenza A acute respiratory failure and hemodynamic shock despite failure of best supportive care. All three survived with “good functional recovery.”

Ruxolitinib is a JAK/STAT pathway inhibitor which is FDA approved for polycythemia rubra vera, myelofibrosis and graft versus host disease. Kenderion et al⁹ reported a murine model of CRS following CAR-T cellular therapy with marked elevation of IL-6, interferon-gamma, TNF alpha mimicking human CAR-T therapy induced CRS. Ruxolitinib treated mice demonstrated clinical amelioration and decrement in inflammatory cytokines. Incyte Corporation has announced plans to launch a Phase III trial of single agent ruxolitinib for COVID-19 associated cytokine storm.

This protocol will evaluate the efficacy of TPE alone or in combination with ruxolitinib in COVID positive patients with PENN grade 2, 3, 4 CRS. It is hypothesized that dual intervention of acute aphaeretic depletion of cytokines and concomitant suppression of production will produce superior amelioration of the cytokine load and to help to prevent cytokine load rebound. This protocol is envisioned as a pilot study (n=20) for hypothesis generation for future investigation.

Primary Endpoints

1. To document the efficacy of TPE alone or in conjunction with ruxolitinib in decreasing the cytokine load over a 14-day intervention study
2. Analysis of all therapy related adverse events (AEs)

Secondary Endpoints

1. To correlate the clinical course of participants with the degree of specific cytokine reductions
3. To calculate time to independence from mechanical ventilation
4. To calculate time to independence from supplemental oxygen therapy

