5. To measure CRP, ferritin and cytokine levels (IL-6, IL-8, IL-10, TNF α , IFN γ , GM-CSF) to map the cytokine landscape over the course of the study
6. To explore correlative biomarker studies
7. To bank plasma and other blood derivatives in the Prisma Health ITOR Biorepository for future investigation

Study Design

Study type:	Interventional Pilot Clinical Trial
Estimated Enrollment	20 patients
Allocation	Two sequential cohorts, 10 patients per cohort First 10 patients will receive TPE alone (Cohort 1A) Second 10 patients will receive TPE in combination with ruxolitinib
Masking	None (open label)
Primary purpose	Treatment efficacy
Official title:	Interventional Study to Evaluate the Efficacy of Therapeutic Plasma Exchange (TPE) Alone or in Combination with Ruxolitinib in COVID-19 Positive Patients with PENN Grade 2, 3, 4 Cytokine Released Syndrome (CRS)

Study Population

COVID-19 positive patients with PENN grade 2, 3, 4 CRS and respiratory failure.

Eligibility

Inclusion:

1. Patients positive for COVID-19 by PCR or alternative accepted methodology
2. PENN class 2,3,4 CRS¹⁰
3. Respiratory insufficiency with supplemental oxygen to maintain O2 sat greater than 89%
4. Clinically positive imaging by CXR or CT scan with evidence of bilateral pulmonary infiltrates, ground glass opacification or other pattern of consolidation felt likely to be linked to COVID infection or complication thereof
5. Adults 22 years of age or older

Exclusion:

1. Pregnancy
2. Breast feeding
3. Class 3-4 NYHA heart failure
4. Current use of synthetic disease modifying anti-rheumatic drugs (DMARDs), with the exception of hydroxychloroquine, or IL-6 inhibitors or other immunosuppressive therapies outside of number five below
5. Current use of chronic corticosteroids if in excess of prednisone 10mg per day or equivalent
6. Suspected or confirmed clinically significant bacterial infection
7. History of TB
8. History of HIV
9. History of IBD
10. JAK inhibitor use within last 30 days
11. Creatinine clearance less than 15 ml / min
12. Absolute neutrophil count < 1000
13. Platelet count < 50,000
14. AST or ALT > 5 times the upper limit of normal
15. Clinical assessment that TPE or ruxolitinib could pose unacceptable risk by study participation or the treatment is deemed inappropriate by a study investigator
16. Current enrollment on another investigational protocol for COVID-19 induced CRS

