The proposed patient population is not anticipated to be at an increased risk compared to a clinically similar population without COVID-19 infection. The device and drug will be used as marketed. Standard risks for the device and drug are outlined in the patient informed consent document. Risks will be minimized by conducting the trial in the inpatient setting of an acute care hospital with dedicated and trained therapeutic apheresis staff, licensed medical personnel and experienced research team members under the direction and oversight of the principal investigator. In the event of patient status improvement, discharge will be acceptable after completion of therapeutic plasma exchange. Daily outpatient follow-up through patient completion of study required assessments will occur in a dedicated phase I research unit.

Removal of medications with TPE is a risk. However, consultation with a hospital pharmacist will occur as needed to determine if a change in timing of medication administration is needed or if medication reloading should occur post TPE.

Dose Modifications

The starting dose of ruxolitinib is 5mg po bid. The need for dose adjustments will be assessed on a daily basis by the research team and pharmacist.

- AST/ALT > 5x ULN, reduce dose of ruxolitinib to 5mg po once daily¹¹
- Platelet count between 25,000 and 35,000, reduce dose of ruxolitinib to 5mg po once daily. Platelet count < 25,000, hold ruxolitinib. May resume once platelet count >25,000 with dosing based on actual platelet count.
- Absolute neutrophil count < 500, hold ruxolitinib until > 500 then resume at full dose
- Creatinine Clearance <15ml/min, discontinue ruxolitinib

Duration of Investigations

A six month patient recruitment period is anticipated. Patient participation is 15 days in duration. An additional six month period of data analysis is anticipated for an overall period of investigation equaling 12 months

Treatment Discontinuation

Treatment discontinuation will occur under the following conditions:

- The patient withdraws consent either from treatment or from the study
- The patient is lost to follow-up
- The patient experiences a side effect that per the protocol requires treatment to end
- The physician deems treatment discontinuation is in the best interest of the patient
- The patient is found to be eligible to participate in the study after being enrolled and continued treatment in this study is not in the best interest of the patient

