- The patient is found to be pregnant or intends to become pregnant
- The patient is noncompliant with the study requirements your disease worsens

Data Handling and Recordkeeping

The principal investigator will carefully monitor study procedures to protect the safety of research subjects, the quality of data, and the integrity of the study. All study subject material will be assigned a unique identifying code or number. The key to the code will be kept in a locked file in the Research Division of the Prisma Health Cancer Institute.

Data Collection, Analysis and Outcomes

REDCap EDC software will be used for data management and future statistical analysis. Designated Cancer Institute research staff will perform extraction of patient records.

Overall Response Rate (ORR) will be defined as $\geq 33\%$ decrease in the cytokine load from peak value through study day 14 in one-third or more participants.

Ethical Considerations

This study will be conducted in accordance will all applicable government regulations and Prisma Health research policies and procedures. This protocol and any amendments will be

submitted and approved by the Prisma Health Institutional Review Board (IRB) prior to any study activity.

All study participants will provide informed consent allowing for their tissue and de-identified clinical information to be used for research purposes.

Safety Monitoring and Reporting

A Drug Safety Monitoring Board (DSMB) will be established consisting of a hematologist, pulmonologist and infectious disease specialist not associated with the research team for this investigation. The committee will review all serious adverse events within 48 hours and will review all patient outcomes for cohort 1a before proceeding to enrollment of cohort 1b.

Adverse Events

Adverse events (AEs) are defined as an unexpected medical problem that happens during treatment with a drug or other therapy. The NCI Common terminology criteria for adverse events (CTCAE Version 5.0) will be used as the standardized severity grading system. AEs will also be reported by degree of relatedness as not related, possibly related, likely related or related to the study drug or study therapy.

SAE Reporting to Incyte

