The Principal Investigator (PI) must report all Serious Adverse Events (SAEs) to Incyte within 24 hours of learning of an event, regardless of the PI's causality assessment. This notification will be provided on a completed Serious Adverse Event (SAE) form. SAE reporting for each subject begins the day the informed consent is signed by the patient and within 30 days after subject has completed or discontinued from the study or has taken last dose of the study drug, or as described in the protocol.

SAEs, occurring using Incyte study drug, are reported in accordance with the effective protocol. SAEs occurring with any other commercial drug are reported to the manufacturer of that drug in accordance with regulations and protocol.

Initial SAEs and/or subsequent follow-up reports will be reported via email to [contact] or fax (+) [name]. SAE reports should be for a single subject. SAE forms should be sent with a cover sheet and any additional attachments.

All adverse event information is reported to Incyte on MedWatch Form FDA 3500A. The Principal Investigator does not provide medical records (e.g., discharge summary) to Incyte, unless specifically requested.

In addition, all SAEs will be reported to the Prisma Health IRB per the institutional policy for reporting.

Reporting of Pregnancy to Incyte

An "Initial Pregnancy Report" or equivalent must be completed in full and emailed to [contact] or faxed to (+) [name] within 24 hours of discovery of a pregnancy of a subject who has taken the Incyte product or the pregnancy of a partner

for a subject who has taken the Incyte product. The “Follow-up Pregnancy Report Form” or equivalent must be completed and emailed to [contact] or faxed to (+) [name] within 30 days after delivery, so that Incyte is provided with information regarding the outcome of the pregnancy. If the pregnancy results in any events which meet the serious criteria (i.e., miscarriage or termination), the SAE reporting process needs to be followed and the timelines associated with a SAE should be followed.

Statistical Analyses

General Statistical Considerations

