Standard statistical methods will be employed to analyze all data. It is anticipated that the following techniques may be used: descriptive statistics, t-test, Chi-square, Fisher’s exact test, Kaplan-Meier analysis, and graphical displays. This protocol may not reflect all analyses planned for the study; additional analyses may be conducted for observational purposes only.

Summary statistics will consist of numbers and percents of responses in each category for discrete measures, and of mean, n, standard deviation, median, minimum, maximum and 95% confidence intervals for continuous measures.

Sample Size Determination

The initial sample size is 20. Each cohort will enroll 10 patients. This number is considered sufficient for an exploratory pilot study to provide information for planning further investigations.

Analysis of Safety

The safety evaluation will compare the proportion of Subjects in each treatment group who exhibit treatment-related adverse effects. These adverse events will be presented for individual patients as a listing of events.

Dissemination of Results

Results of this study may be used for presentations, posters, publications, or extramural grant applications. The publication will not contain any identifiable information that could be linked to a study patient.

References

<https://doi.org/10.1038/s41586-020-2012-7>
2. World Health Organization. Novel coronavirus situation report-2. January 22, 2020.
<https://www.who.int/docs/default-source/coronavirus/situation-reports/20200122-sitrep-2-2019-ncov.pdf> (Accessed on April 7, 2020).
3. P. Conti, G. Ronconi, A. Caraffa, C. Gallenga, R. Ross, I. Frydas, S. Kritas. Induction of pro-inflammatory cytokines (IL-1 and IL-6) and lung inflammation by COVID-19: anti-inflammatory strategies. *J Biol Regul Homeost Agents*. 2020 Mar 14; 34(2).
4. Puja Mehta, Daniel F McAuley, Michael Brown, Emilie Sanchez, Rachel S Tattersall, Jessica J Manson. COVID-19: consider cytokine storm syndromes and immunosuppression. *The Lancet*. 28 March–3 April 2020.

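### No rule says how a patient who dies on support enters the two time-to-independence endpoints, and the usual Kaplan-Meier convention would overstate the proportion freed (minor)

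*Combined protocol and SAP*

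**What the plan says.** The Secondary Endpoints section gives each endpoint one line: "To calculate time to independence from mechanical ventilation" and "To calculate time to independence from supplemental oxygen therapy". Neither line mentions death, censoring or a horizon.

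General Statistical Considerations is the only analysis text that bears on them. It lists techniques that may be used, ending with "Kaplan-Meier analysis, and graphical displays", and assigns none to an endpoint. Kaplan-Meier is the only time-to-event method in the list.

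The Study Population section describes "COVID-19 positive patients with PENN grade 2, 3, 4 CRS and respiratory failure". Entry requires "Respiratory insufficiency with supplemental oxygen to maintain O2 sat greater than 89" percent, and Appendix B has separate rows for ventilated and non-intubated patients. The ventilation endpoint may therefore rest on fewer than 10 patients per cohort.

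Deaths should be known to the study. Under Safety Monitoring and Reporting, "The committee will review all serious adverse events within 48 hours"; under SAE Reporting to Incyte, "all SAEs will be reported to the Prisma Health IRB". After discharge, the Risk Analysis section says "Daily outpatient follow-up through patient completion of study required assessments will occur in a dedicated phase I research unit".

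The treatment discontinuation list, the statistical section and both schedules in Appendix B are silent on how a death enters these two estimates. That statement covers only the text available: part of the document was removed before review, and the visible secondary endpoints are numbered 1, 3, 4 onward.

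**The concern.** A patient who dies while ventilated or on oxygen will never become independent of that support. Censoring at death treats the patient as someone who would have gone on to be freed at the same rate as those still at risk. Kaplan-Meier then passes that patient's weight to later recoveries. The resulting figure can equal or exceed the true proportion freed, but it cannot fall below it.

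In a population with respiratory failure, deaths on support are foreseeable. The pilot's stated use is to inform the planning of later studies, and an inflated recovery proportion is a poor input for that. It also weakens a descriptive look across cohorts, because a death-censored curve follows the recovery rate among those still at risk and does not show that more patients died in one cohort.

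**Working it through.** **Figure to reproduce.** There is none. The sample size of 20 is 2 × 10 without a formula, and no figure is given for these endpoints.

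**Inputs.** From the documents: 10 patients per cohort, and daily respiratory rows that cover days 1-14 in both schedules. Assumed, because the documents give no values: the numbers freed and dead, and no withdrawal or loss before day 14.

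**Step 1: bounds for 10 patients.** Let n be the number at risk, f the number freed and d the number dead on support by day 14. The remaining patients are on support at day 14. The true proportion freed is f/n.

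- If no death precedes a recovery, every recovery occurs with the full risk set, so 1-KM = f/n and the gap is zero.
- If all deaths come first, the risk set at the first recovery is n − d. The product of survival factors collapses to (n − d − f)/(n − d), so 1-KM = f/(n − d).
- All other orderings lie between these limits.

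| Freed / dead of 10 | True | 1-KM, no death before a recovery | 1-KM, all deaths first |
|---|---|---|---|
| 6 / 1 | 60% | 6/10 = 60% | 6/9 = 67% |
| 5 / 3 | 50% | 5/10 = 50% | 5/7 = 71% |
| 4 / 4 | 40% | 4/10 = 40% | 4/6 = 67% |

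**Step 2: one ordering in full (illustrative only).** Freed on days 3, 6, 9, 12; dead on days 2, 5, 8, 11; two on support at day 14. With deaths censored, the risk sets at the four recoveries are 9, 7, 5 and 3:

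KM = 8/9 × 6/7 × 4/5 × 2/3 = 0.406, so 1-KM = 59%, with a median of 12 days.

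With deaths kept at risk as never freed, the result is 4/10 = 40% and the median is not reached. Cumulative incidence with death as a competing event also gives 40%. This is one constructed ordering within the 40-67% range, not a typical case.

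**Step 3: constant hazards.** Let λ be the hazard of being freed and μ the hazard of death on support. With true proportions F freed and D dead at time t, exp(−(λ+μ)t) = 1 − F − D and λ/(λ+μ) = F/(F+D). The death-censored estimate is 1 − exp(−λt) = 1 − (1 − F − D)^(F/(F+D)).

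| F / D | Calculation | 1-KM | Gap (points) |
|---|---|---|---|
| 60 / 10 | 1 − 0.30^(6/7) | 64.4% | 4.4 |
| 60 / 20 | 1 − 0.20^0.75 | 70.1% | 10.1 |
| 50 / 30 | 1 − 0.20^0.625 | 63.4% | 13.4 |
| 40 / 40 | 1 − 0.20^0.5 | 55.3% | 15.3 |
| 30 / 50 | 1 − 0.20^0.375 | 45.3% | 15.3 |

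**Step 4: two cohorts.** The expression 1 − exp(−λt) does not contain μ. Take λt from the 60/20 row: 0.75 × (−ln 0.20) = 1.207. A cohort with that recovery hazard and no deaths truly frees 1 − exp(−1.207) = 70.1%. The 60/20 cohort truly frees 60%. The death-censored curve reads 70.1% for both.

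**Step 5: scale against sampling error.** The exact 95% interval for 4/10 is 12-74%.

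**The case against.** The strongest reply is about weight. These are secondary endpoints in a hypothesis-generating pilot; no test, threshold or decision rests on them; and the gaps sit well inside an interval of 12-74%. With one death in ten, no ordering gives a gap as large as 7 points, and with no deaths there is no gap. All of this stands and is why the point is minor. It does not remove the point, because a bias in one direction is not cancelled by a wide interval.

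A second reply is that deaths would not be hidden. Serious adverse events are reported and reviewed, and the safety board looks at all cohort 1A outcomes before cohort 1B enrols. This also stands. Knowing of a death, however, does not settle how it enters these estimates.

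A reader might infer that the listed techniques conflict, for example that a t-test or a median among freed patients only could be set against Kaplan-Meier and reverse the comparison between cohorts. Data can be constructed to show this, but the documents do not support it as a finding. They never propose a freed-only summary or a test for these endpoints, and the natural reading pairs them with the one time-to-event method named. Nor is Kaplan-Meier itself at fault, since it gives the right proportion if deaths stay in the risk set.

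**Conclusion.** The point holds as a minor one. The plan leaves out one coding rule, and under the usual convention the omission can only push the proportion freed upward. The size depends on mortality, which is assumed here: the gap runs from zero to 7, 21 or 27 points in the three 10-patient cases, and from about 4 to 15 points under constant hazards with freed/dead from 60/10 to 30/50. Those figures also assume complete follow-up to day 14.

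The time origin, the ventilation risk set and the handling of a return to support are also unstated. A reader might count these as further faults. They are ordinary missing detail, and the schedules already label the ventilator rows as applying to ventilated patients only. The effect on the trial's conclusions is limited.

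**What to change.** Add to the Statistical Analyses section:

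- Both endpoints are estimated by cumulative incidence (Aalen-Johansen) with death on support as a competing event, or by Kaplan-Meier with deaths kept at risk as never freed to the horizon. The two give the same proportion when follow-up is complete.
- Only withdrawal, loss to follow-up and being alive on support at the horizon are censored.
- One horizon applies to both cohorts. Day 14, counted with first TPE as day 1, is covered by the daily respiratory rows in both Appendix B schedules. Status at the day 28 visit can be reported in addition.
- The number of deaths is reported beside each estimate.

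The cost is a few sentences and no new data: support is recorded daily, follow-up continues after discharge, and deaths should arrive through SAE reporting. The downside is a less favourable proportion freed, by about 4 to 15 points in the constant-hazard scenarios above, and a median that may not be reached.

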17. Stage 4 obstructive lung disease with chronic hypoxic respiratory failure requiring supplemental O2 at baseline, or ILD with chronic hypoxic respiratory failure requiring supplemental O2 at baseline

Treatment Plan

Device: Spectra Optia Apheresis System

Intended Use of Device: Therapeutic Plasma Exchange performed per marketed labeling

Drug: Ruxolitinib (generic) marketed as brand name, Jakafi ,manufactured by Incyte Corporation, will be used per the marketed package insert.

Cohort 1A: TPE, five single plasma volume exchanges over 7 days (every day x 2 then every other day x 3) with albumin or FFP replacement if underlying coagulopathy per institutional protocol (Appendix A).

Other – standard medical care

Cohort 1B: TPE as in cohort 1A combined with ruxolitinib 5mg po BID beginning day prior to first TPE and continuing BID for total of 14 days. On days of TPE, ruxolitinib dosing will be immediately post procedure and a second dose approximately 8 hours later.

Other – standard medical care

Schedule of Assessments

Pre Treatment

Standard of Care Assessments

- Complete Blood Count (CBC)
- Comprehensive Metabolic Panel (CMP)
- C-Reactive Protein (CRP)
- Ferritin
- lipid panel
- Hepatitis B Surface Antigen, Hepatitis B Surface Antibody, Hepatitis B Core Antibody and Hepatitis C Antibody
- PT/INR
- Partial Thromboplastin Time (PTT)
- Fibrinogen
- type and screen
- serum pregnancy test
- physical examination

Study Related Assessments

- cytokine panel
- peripheral blood for biorepository
- peripheral blood for pharmacogenomics

During Treatment (On Study)

Standard of Care Assessments

- daily CBC
- daily CRP
- PaO₂/FiO₂ ratios days (with ABGs) per Appendix B
- amount of supplemental O₂, SPO₂%, respiratory rate, imaging per MD discretion (*for non-intubated patients*)
- measure daily SPO₂%, FiO₂; PEEP; and lung compliance (inspiratory pause – V_t/P_{plat} – PEEP) or plateau pressures (*mechanically vented patients*)
- daily Basic Metabolic Panel (BMP)
- physical examination

Study Related Assessments

- daily collection of study related adverse events and/or serious adverse events
- Fibrinogen (on days of TPE only)
- daily cytokine panel and GM-CSF
- repeat cytokine panel and GM-CSF within 60 minutes post TPE (on days of procedure only)
- serum ferritin per Appendix B
- peripheral blood and plasma waste for biorepository per Appendix B
- day 28 office visit or virtual health visit to assess clinical status of the patient

Risk Analysis

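### The only planned cohort safety comparison counts treatment-related events, judged without masking and with one more candidate agent in Cohort 1B, so it can be biased, plausibly against 1B.

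*Combined protocol and SAP*

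**What the plan says.** All references are to the combined protocol and SAP.

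- **Comparison.** Analysis of Safety will "compare the proportion of Subjects in each treatment group who exhibit treatment-related adverse effects". It then says: "These adverse events will be presented for individual patients as a listing of events". Read literally, the listing covers the same related-only subset.
- **Endpoint.** The second primary endpoint is likewise restricted to therapy-related adverse events.
- **Collection.** The on-study part of Schedule of Assessments specifies "daily collection of study related adverse events and/or serious adverse events".
- **Relatedness.** Under Adverse Events, events are graded by CTCAE v5.0 and "reported by degree of relatedness as not related, possibly related, likely related or related to the study drug or study therapy". No level on that four-point scale is set as the threshold for treatment-related.
- **Assessor.** The only causality assessor mentioned is the principal investigator, and only for serious events, which go to the manufacturer "within 24 hours of learning of an event, regardless of the PI's causality assessment". No assessor is named for non-serious events, and no masked or independent adjudication is described.
- **Design.** There are two sequential, non-randomised cohorts of 10 without masking: TPE alone (1A), then TPE plus ruxolitinib (1B).

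**The concern.** A between-group comparison needs an outcome measured in the same way in both groups. Here the outcome passes through a causality opinion formed with the treatment known, and the set of candidate causes differs by cohort. A fall in platelets in 1A can be assigned to the exchange, or to COVID-19, standard care or nothing in particular. In 1B the same fall can also be assigned to ruxolitinib. If that extra option makes a related call more likely, 1B shows more related events at identical toxicity.

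This is a defect of the measure. It is separate from the lack of randomisation and from the small numbers, and recording every event would not cure it while only the related ones are compared. At stake is the between-cohort reading of a primary endpoint in a pilot meant to inform the planning of later studies of the combination.

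**Working it through.** **What can be reproduced.** The plan gives no event rate, attribution rate, alpha or power. The only figure to check is the sample size, 2 × 10 = 20, which agrees. The rest is illustration: n = 10 per cohort is from the plan, and all rates are assumptions.

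**Model 1: one event status per patient.** Let t be the true event rate, equal in both cohorts, and a the probability that an event is called related. The related proportion is p = t × a. With independent counts X_A ~ Bin(10, p_A) and X_B ~ Bin(10, p_B),

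P(X_B − X_A ≥ 3) = Σ P(X_A = i) P(X_B = j), summed over all j ≥ i + 3.

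| Assumed t; a in 1A v 1B | Related, 1A v 1B | P(1B exceeds 1A by ≥ 3) |
|---|---|---|
| equal attribution | 10% v 10% | 0.03 |
| equal attribution | 25% v 25% | 0.10 |
| equal attribution | 50% v 50% | 0.13 |
| 50%; 40% v 60% | 20% v 30% | 0.22 |
| 40%; 25% v 75% | 10% v 30% | 0.38 |
| 60%; 30% v 70% | 18% v 42% | 0.48 |
| 50%; 20% v 80% | 10% v 40% | 0.61 |

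The first three rows are the chance baseline. True toxicity is equal in every row. By symmetry, related proportions of 30% v 20% give 0.22 for a spurious excess in 1A.

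**Model 2: k events per patient.** Let each event be called related with probability q in 1A and 1 − (1 − q)(1 − r) in 1B, where r is the extra attribution to ruxolitinib. The proportion of patients with at least one related event is 1 − (1 − per-event probability)^k. Take k = 2 and q = 0.2.

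- 1A: 1 − 0.8² = 36%.
- r = 0: 1B is also 36%, and P(1B > 1A) = 0.41.
- r = 0.1: per event 1 − 0.8 × 0.9 = 0.28; 1B is 1 − 0.72² = 48%; P(1B > 1A) = 0.63.
- r = 0.2: per event 1 − 0.8 × 0.8 = 0.36; 1B is 1 − 0.64² = 59%; P(1B > 1A) = 0.80.
- Reversal: if per-event attribution is 0.3 in 1A and drifts down to 0.2 in 1B, the proportions are 1 − 0.7² = 51% v 36%, and P(1B > 1A) = 0.18.

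**With an all-cause comparison.** At equal true toxicity the expected difference is zero whatever the attribution. At a 50% event rate, P(1B > 1A) = P(1B < 1A) = 0.41, the remainder being ties.

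**The case against.** The strongest case against is as follows.

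- **No attribution gap is documented.** This stands. With r = 0 there is no bias, and with drift the sign changes. A reader might infer that equal toxicity will show up as excess harm from ruxolitinib. The documents do not support that: they give no attribution rate, COVID-19 competes as an explanation in both cohorts, and the plan nowhere says that a cohort difference will be read as a ruxolitinib effect.
- **The dose-modification rules do not steer attribution.** A reader might infer that they do, because they name platelets, neutrophils, AST/ALT and creatinine clearance for ruxolitinib. They are dosing thresholds and give no guidance on causality, so this is conjecture.
- **The assessor is not stated to be an unmasked investigator.** For non-serious events this is correct, since none is named. But nothing in an open-label plan without adjudication masks whoever makes the call.
- **Other safeguards exist.** Relatedness is reported on a scale that includes unrelated events. An independent safety board reviews all serious events, which also go to the manufacturer and the IRB whatever their cause. Additional analyses are allowed. All true, but none changes what Analysis of Safety compares, and the board is not asked to adjudicate relatedness.
- **Stakes are low.** This stands in part. The study is a 20-patient pilot and no decision rule uses this contrast. Even at 10% v 40%, a two-sided Fisher test at an assumed 0.05 level would be significant against 1B only 15% of the time. The risk is a misleading descriptive signal carried into planning.

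**Conclusion.** The point holds in limited form. The specified comparison is filtered on an unmasked relatedness judgement with an extra candidate cause in one cohort, so it can be biased. The likelier direction is against 1B, but the reverse is possible and the filter can also hide harm if events are written off to COVID-19.

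The size is not known. Against a chance baseline of 0.03 to 0.13, the probability of a spurious excess of 3 or more patients in 1B is 0.22 for a 10-point difference in related proportions (20% v 30%) and 0.61 for a 30-point difference (10% v 40%). The last figure needs an assumed attribution gap of 60 percentage points (20% v 80% at a 50% event rate) and should be read as an upper illustration. These figures rest on independent patients, equal true toxicity and complete cohorts of 10.

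The change is worth making because it concerns a primary endpoint and is cheap. It will not isolate a ruxolitinib effect, since cohort and calendar time are confounded under any event definition.

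**What to change.** 1. **Analysis of Safety.** Compare the cohorts without regard to attribution: patients with any adverse event, with any event of grade 3 or higher, and with any serious event, each with an exact confidence interval. The interval shows how little 10 patients can say: 3 of 10 gives 7% to 65%.
2. **Laboratory comparison.** From the daily CBC and BMP in Appendix B, and fibrinogen on exchange days (1, 2, 4, 6 and 8 in both cohorts), compute the worst on-study CTCAE v5.0 grade and the shift from screening. State one window of equal length. Appendix B numbers the daily visits 1 to 15 in 1A and 0 to 14 in 1B, which is 15 days from first study treatment in each.
3. **Relatedness.** Keep it as a descriptive column, recorded separately for TPE and for ruxolitinib. State who judges it and which levels count as related.
4. **Schedule of Assessments.** Reword the daily collection item so that all adverse events are captured regardless of relatedness. As written, the filter may already act at collection, and then item 1 could not be delivered for non-serious events.

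**Cost.** Revised wording in two sections, a grading program, and somewhat more event recording; no new blood draws. Disease-related events will dilute the contrast. The laboratory comparison has no liver component: Appendix B schedules the CMP at screening only, and although the Appendix A plasma-replacement orders list it daily, the albumin orders do not. The comparison remains descriptive because the cohorts are sequential and non-randomised.
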